5.2 RECORDING AND REPORTING OF ADVERSE EVENTS

Any adverse events will be reviewed by clinicians and recorded from the point of consent to the end of infusion plus 24 hours. Any serious adverse events should be reported as indicated in section 5.3.

We will record any new grade 3 or 4 laboratory abnormalities (CTCAE) in Haemoglobin, Neutrophil count, Alanine aminotransferase (ALT), Potassium, Sodium, as adverse events in addition to any clinically significant untoward medical occurrence. Lymphopaenia is well reported in COVID-19 infection and therefore will not be recorded¹ (Table 2).

We will also specifically record any incidence of deep vein thrombosis or myocardial infarction.

Routine observations, D-dimer, Platelets, aPTT, Fibrinogen, INR, Plasma Renin Mass, Bilirubin, LDH, Haptoglobin, Creatinine, BNP, Ferritin, Troponin, Pro-calcitonin and Glucose will all be recorded as study endpoints and therefore not recorded separately as adverse events.

Medical judgement will be used to determine clinical significance and the need to record other events as AEs. Other non-serious events below CTCAE grade 3-4 or other known symptoms of COVID-19 would not normally be considered clinically significant for the purposes of AE reporting in this study.

Table 2.

CTCAE Term	Grade 3	Grade 4
Alanine aminotransferase (ALT) Male 0-45 unit/L Female 0-34 unit/L	Male (225 – 900), Female (170 – 680) if baseline was normal; >5.0 - 20.0 x baseline, if baseline was abnormal	Male (>900), Female (>680) if baseline was normal; >20.0 x baseline if baseline was abnormal
Anaemia (Hgb) Male 130-168 g/L Female 114-150 g/L	Hgb <80 g/L; transfusion indicated	Life-threatening consequences; urgent intervention indicated
Haemoglobin increased	Increase in >40 g/L	-
Neutrophil count decreased 2.0-7.1 x10 ⁹ /L	<1.0 - 0.5 x 10 ⁹ /L	<0.5 x 10 ⁹ /L
Hyperkalemia 3.5-5.3 mmol/L	>6.0 - 7.0 mmol/L; hospitalisation indicated	>7.0 mmol/L; life-threatening consequences
Hypokalemia 3.5-5.3 mmol/L	<3.0 - 2.5 mmol/L; hospitalisation indicated	<2.5 mmol/L; life-threatening consequences
Hypernatremia 133-146 mmol/L	>155 - 160 mmol/L; hospitalisation indicated	>160 mmol/L; life-threatening consequences
Hyponatremia 133-146 mmol/L	125-129 mmol/L symptomatic; 120-124 mmol/L regardless of symptoms	<120 mmol/L; life-threatening consequences


Any adverse events should be recorded in the CRF. Depending on the nature of the event the reporting procedures below should be followed. Any questions concerning adverse event reporting should be directed to the Chief Investigator in the first instance.

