3. STUDY DESIGN

The proposed study will be run as a double-blind, randomized controlled experimental medicine study in male and female hospitalised patients (n=60) aged 18 or over, with confirmed COVID-19 infection. Patients who are admitted with confirmed COVID-19 infection will be screened with a routine medical assessment (see Table 1) and enrolled if they meet the eligibility criteria. Subjects will be block randomised based on age to continuous intravenous infusion of placebo or TRV027 for 7 days.

Day 1 procedures can occur on the same day of screening and include a venous blood test prior to commencing an intravenous infusion of either placebo (250ml sodium chloride 0.9%) or TRV027 in 250ml sodium chloride 0.9% at 12mg/hr. The infusions will continue for 7 days. Venous blood tests will be repeated at days 3, 5 and 8 amounting to approximately 120mLs of blood in total over the 8-day period.

Once the infusion has finished, the subjects will remain in hospital for a further 24 hours for vital signs and adverse event monitoring. If the infusion is stopped before the 7-day dosing period finishes, they will be advised to remain in hospital for a 24-hour period for monitoring during which time the study assessments will continue. If discharge is planned for day 6 or 7 the day 8 blood tests can be taken on the day of discharge. They will also be followed up at Day 30 either by telephone call or through examination of medical records.

Table 1: Schedule of Study Events

Study Day	*Screening	*1	2	3	4	5	6	7	8	9	30
Informed consent (or agreement from consultee if incapacitated)	X										
Eligibility assessment; routine medical assessment (history, observations)	X										
Review of Concomitant Medications ¹		X	X	X	X	X	X	X	X		
Pregnancy test (If appropriate)	X										
Venous blood test for primary and exploratory endpoint assessment:											
D-dimer		X		X		X			X		
Platelets		X		X		X			X		
aPTT		X		X		X			X		
INR		X		X		X			X		
Fibrinogen		X		X		X			X		
Plasma Renin Mass		X									
Total Bilirubin		X		X		X			X		
LDH		X		X		X			X		
Haptoglobin		X		X		X			X		
Creatinine		X		X		X			X		
BNP		X		X		X			X		
Troponin		X		X		X			X		
Ferritin		X		X		X			X		
Pro-calcitonin		X		X		X			X		
Glucose		X		X		X			X		
Clinical assessment for exploratory endpoints											
Inotrope requirement		X		X		X			X		
GCS		X		X		X			X		
SOFA score		X		X		X			X		
Randomisation		X									
Infusion		X	X	X	X	X	X	X	X		
Vital signs monitoring four times a day		X	X	X	X	X	X	X	X	X	

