Adverse event monitoring		X	X	X	X	X	X	X	X	X	
Telephone call or medical record check											X

[figure not shown]
*Screening and day 1 can be combined

1. All concomitant medications will be reviewed at baseline but only those which affect eligibility or are associated with AEs will be recorded for subsequent days in the Ecrf. ACEi and aldosterone antagonists will be recorded.

Dose Rationale

TRV027 has been studied in patients with acute heart failure in doses ranging from 1.25 – 31.25 mg/hr. Using in vitro-derived AT1R receptor binding data as well as population PK data in healthy volunteers, simulations were performed to explore a range of doses of TRV027 which might be expected to result in at least 80% receptor occupancy, correcting for protein binding. The results (Figure 1) suggest that 12 mg/hr will result in median receptor occupancy well in excess of 80%. This dose is in the mid-range of what has been studied clinically and is expected to be well tolerated.

Figure 1: Estimation of the median AT1R receptor occupancy resulting from TRV027 given at a dose of 12 mg/hr for 96 hours

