3.6 Mortality data

Patient survival status will be monitored up to day 30 and tabulated in Table 9.

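### Adverse event recording ends 24 hours after each patient's own infusion and nothing is specified for Day 30, so the arms can be compared over unequal windows if early stopping differs

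*Protocol*

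**What the plan says.** - **Recording window.** Protocol 5.2 has adverse events "recorded from the point of consent to the end of infusion plus 24 hours".
- **Length of infusion.** Protocol section 3: "The infusions will continue for 7 days". After that "the subjects will remain in hospital for a further 24 hours for vital signs and adverse event monitoring".
- **Early stop.** Protocol section 3: "If the infusion is stopped before the 7-day dosing period finishes, they will be advised to remain in hospital for a 24-hour period for monitoring". The 24 hours run from the actual stop, and staying is advised, not required.
- **Schedule.** In the protocol's Table 1 the row "Adverse event monitoring" is marked on Days 1 to 9 and not on Day 30.
- **Day 30.** Protocol section 3: "They will also be followed up at Day 30 either by telephone call or through examination of medical records". No adverse event content is given for that contact. SAP 3.6: "Patient survival status will be monitored up to day 30", with SAP Table 9 offering alive, dead or lost to follow-up.
- **Thrombosis.** Protocol 5.2: "We will also specifically record any incidence of deep vein thrombosis or myocardial infarction". This sentence has no time limit of its own, and it names neither pulmonary embolism nor stroke.
- **SAEs.** Protocol 5.3 requires all of them to be recorded and states no end date.
- **Safety tables.** SAP 3.4 with Tables 3 and 6 gives numbers of events and of subjects by arm. It states no fixed window and no person-time.

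**The concern.** The end of a patient's recording window is set by the end of that patient's infusion, which can itself be an outcome. The plan foresees this. SAP 3.5 allows for infusions shorter than 7 days, SAP Table 2 has rows for doses missed through discharge and through death, and SAP 2.5 lists toxicity among the withdrawal reasons. A patient who stops because of a drug effect is then watched for less time than one who completes. If that happens more often in one arm, its counts fall for a reason unrelated to safety. If one arm is discharged earlier because it recovers faster, its counts fall for that reason too.

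The second issue is what happens between the end of the window and Day 30. The study is about coagulopathy, and the protocol singles out two thrombotic events for recording. Yet neither document says that the Day 30 contact asks about them. The DSMC reviews safety after every 12 patients, and Protocol section 7 says aggregate data will inform the design of later studies of RAS modulators, TRV027 included. The safety counts will therefore be used.

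**Working it through.** **Inputs from the documents.** Infusion 7 days, plus 24 hours (Protocol 3 and 5.2); final contact at Day 30 (Protocol 3); 30 patients per arm (Protocol 7); 72 hours counted as complete for the primary endpoint (SAP 3.5). Stopping shares, event risks and hazard shapes are not in the documents and are assumed below. Windows are counted from the start of infusion; any time between consent and infusion is extra.

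**1. Reproducing the schedule.** Day 1 + 7 days + 1 day = Day 9, which matches the last mark in Table 1. The two passages agree for a full course.

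**2. Window by infusion length.** Window = infusion days + 1. Day 1 to Day 30 is 29 days.

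| Infusion | Window | Last day | Share of 29 days | Days outside |
|---|---|---|---|---|
| 2 days | 3 days | Day 4 | 10% | 26 |
| 3 days | 4 days | Day 5 | 14% | 25 |
| 5 days | 6 days | Day 7 | 21% | 23 |
| 7 days | 8 days | Day 9 | 28% | 21 |

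**3. Effect on a comparison of arms with no true difference.** Assume a 10% event risk by Day 30 at constant hazard h = −ln(0.9)/29 = 0.00363 per day. If a share q of an arm stops at 72 hours, its expected number of patients with an event is

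E(q) = 30 × [q(1 − e^(−4h)) + (1 − q)(1 − e^(−8h))].

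- 10% v 10% stopping: 0.82/0.82, ratio 1.00
- 20% v 10%: 0.77/0.82, ratio 0.95
- 30% v 10%: 0.73/0.82, ratio 0.90
- 30% v 0%: 0.73/0.86, ratio 0.85

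In observation time, with 20% v 0% stopping at 48 hours, the loss is 0.2 × (192 − 72)/192 = 12.5%. With the stop at 72 hours it is 0.2 × (192 − 96)/192 = 10%.

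**4. Events outside the window for a patient who completes.** With constant hazard and a 10% risk, 3.0 events are expected in 30 patients by Day 30 and 0.86 in the first 8 days, so 1 − 0.86/3.0 = 71% fall outside (70% to 72% for risks of 20% to 5%). If instead the hazard halves every H days, the share inside is (1 − 2^(−8/H))/(1 − 2^(−29/H)). For H = 3, 5 and 10 days this is 84%, 68% and 49%, so 16%, 32% and 51% fall outside.

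**5. Would rates per patient-day be enough?** Not if risk is concentrated early. With H = 5, 43.3% of the Day 30 events fall in the first 4 days and 68.2% in the first 8. Per day that is 0.433/4 = 0.108 against 0.682/8 = 0.085, a ratio of 1.27. The shorter window now looks worse, again with no true difference.

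**The case against.** A reader might infer that later clots are lost. The text does not go that far. Protocol 5.3 sets no end date for SAEs, and the sentence on deep vein thrombosis and myocardial infarction has no window, so a later serious clot could be recorded. What remains is that no procedure for finding it is stated. In addition, the seriousness criteria in Protocol 5.1 list prolongation of a current stay but not a new admission, whereas SAP Table 6 includes inpatient hospitalisation.

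A reader might also infer that the arms are compared over unequal windows. That is conditional. Windows differ between patients; they differ between arms only if stopping does, and the documents give no stopping rates by arm.

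A third tempting reading is that pulmonary embolism and stroke would be dismissed as COVID-19. Protocol 5.2 also records clinically significant untoward occurrences, which is the more natural place for them. The remaining risk is inconsistent judgement, not exclusion.

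On the defence side:

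- Tables 3 and 6 count subjects as well as events, specify no test, and sit beside compliance data in Table 2. This helps the reader but does not make the windows equal.
- Protocol 1.3 gives a half-life of 4.2 to 15.8 minutes, so 24 hours is at least 1,440/15.8 = 91 half-lives. That supports 24 hours as an on-treatment window for one patient. It does not deal with windows that vary with outcome.
- Thrombosis is not an endpoint in this 60-patient study with a Day 3 primary measure, and a DSMC is in place. This limits the weight of the point.
- Table 1 marks Days 1 to 9 without condition and could be read as a fixed window, but Protocol 3 and 5.2 tie the end to the actual stop.

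**Conclusion.** The point holds in conditional form. As written, how long a patient is observed for adverse events depends on why and when the infusion ended, and the plan specifies no adverse event, SAE or thrombosis collection at Day 30. The size of any distortion between arms depends on unequal stopping: none if stopping is equal, and a null ratio of 0.95 to 0.85 for differences of 10 to 30 percentage points at 72 hours, under an assumed constant hazard and 10% risk. The 12.5% loss of observation time is only an illustration, resting on 20% against 0% stopping at 48 hours. Even after a full course, 21 of the 29 days to Day 30 lie outside the window. The share of events falling there ranges from 16% to 72% across the assumed hazards and risks, so no single figure should be quoted. The primary D-dimer analysis and the sample size are unaffected. This is a worthwhile, inexpensive improvement to safety ascertainment.

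**What to change.** 1. In Protocol 5.2 and 5.3, state Day 30 as the common end date, in both arms, for SAEs and for dated thrombotic events: deep vein thrombosis and myocardial infarction as already named, with pulmonary embolism and stroke added.
2. In Protocol section 3 and Table 1, state that the existing Day 30 call or record check collects these, with dates.
3. In SAP 3.4, add one table of the number of subjects with each event by arm to Day 30, for everyone dosed, to be read alongside the survival table.
4. In SAP 3.4, summarise other adverse events over one fixed window from the start of infusion, the same for all patients. Days 1 to 9, as already marked in Table 1, is an obvious candidate; for patients who leave earlier, the remainder would have to come from the Day 30 contact. Give rates per patient-day only as a supplement, since they assume a roughly constant hazard.

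The cost is a few added questions at a contact already scheduled and one added table. No treatment, visit or sample size changes. The drawback is that information gathered after discharge, by telephone or from records, will be less detailed than inpatient monitoring. This is why the Day 30 table is best limited to SAEs and dated thrombotic events.

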5.3 SERIOUS ADVERSE EVENTS

All such events, whether expected or not, should be recorded.

An SAE form should be completed and faxed to the Chief Investigator within 24 hours. However, relapse and death due to Covid19, and hospitalisations for elective treatment of a pre-existing condition do not need reporting as SAEs.

All SAEs should be reported to the London South East Research Ethics Committee where in the opinion of the Chief Investigator, the event was:

- 'related', i.e. resulted from the administration of any of the research procedures; and
- 'unexpected', i.e. an event that is not listed in the protocol as an expected occurrence

Reports of related and unexpected SAEs should be submitted within 15 days of the Chief Investigator becoming aware of the event, using the NRES SAE form for non-IMP studies. The Chief Investigator must also notify the Sponsor of all SAEs.

Local investigators should report any SAEs as required by their Local Research Ethics Committee, Sponsor and/or Research & Development Office.

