3.4 Safety data

Adverse events (AE) will be summarised by severity (NCI-CTCAE v4.03), classification, expectedness and relationship to the study drug (Table 3) and also described per patient for each treatment groups (Tables 4 and 5), while serious adverse events (SAE) will be summarised by SAE reason, severity, and causal relationship to study drug (Table 6). The details of each SAE will also be listed with the respective SAE term and outcome (Tables 7 and 8).

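### Only deep vein thrombosis and myocardial infarction are named for specific recording; other clots and bleeds rely on general rules that leave three gaps, and the SAP counts no clot or bleed by arm

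*Protocol*

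**What the plan says.** Protocol 5.2 sets out what is recorded as an adverse event (AE):

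- New grade 3 or 4 abnormalities in five laboratory tests, haemoglobin among them, are recorded "in addition to any clinically significant untoward medical occurrence".
- Two clinical events are named: "We will also specifically record any incidence of deep vein thrombosis or myocardial infarction".
- Everything else is left to the site: "Medical judgement will be used to determine clinical significance and the need to record other events as AEs".
- The site is given a steer: "Other non-serious events below CTCAE grade 3-4 or other known symptoms of COVID-19 would not normally be considered clinically significant".

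Protocol 5.3 says of SAEs: "All such events, whether expected or not, should be recorded". It then makes an exception: "relapse and death due to Covid19, and hospitalisations for elective treatment of a pre-existing condition do not need reporting as SAEs".

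Protocol 5.1 defines an AE by reference to 5.2, and makes being unexpected part of the SAE definition.

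On output, SAP 3.4 says: "Adverse events (AE) will be summarised by severity (NCI-CTCAE v4.03), classification, expectedness and relationship to the study drug (Table 3"). Table 6 groups SAEs by reason, severity and causal relationship. Table 4 lists AE category, name and grade for each patient by arm. Tables 7 and 8 list SAE terms and outcomes, one table per arm. Table 9 gives Day 30 survival status only.

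**The concern.** The primary objective is the coagulopathy of COVID-19, and the primary endpoint is a coagulation marker. Clots and bleeds are the clinical events closest to that endpoint, and the likeliest place for a coagulation effect of the drug, good or bad, to show itself. Yet the named list holds one venous and one arterial event. For the rest, recording can turn on whether the site regards the event as part of COVID-19.

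The protocol gives sites some reason to see it that way. Its background section presents coagulopathy and glomerular thrombosis as part of the COVID-19 picture. Section 5.2 leaves lymphopaenia unrecorded because it is already well described in that disease. A site could reason in the same way about a small lung clot.

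At stake is whether the D-dimer result can be set beside a complete clinical record, and whether the safety committee, which meets after every 12 recruits (Protocol 5.4), sees all the relevant events.

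**Working it through.** No figure in the plan bears on this point, so the check is mainly of text: follow each kind of event through the rules.

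**1. Deep vein thrombosis or myocardial infarction, any severity.** Recorded by name under 5.2, whatever the attribution.

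**2. Another clot or bleed, serious but not fatal.** Section 5.1 counts an event as serious if it threatens life, prolongs the stay or disables. It also asks for judgement on events that may need intervention to prevent such outcomes. Section 5.3 then requires recording: "All such events, whether expected or not, should be recorded". Its COVID-19 exemption reaches only relapse and death. Most pulmonary emboli, strokes and major bleeds should therefore be captured. The weak link is the word *unexpected* in the 5.1 definition, which contradicts 5.3. Section 4.4 says many subjects are likely to progress to end organ failure and that intensive care admission is expected. A site working from 5.1 could leave out a complication that it had expected.

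**3. Another clot or bleed, fatal and attributed to COVID-19.** The exemption applies: "relapse and death due to Covid19, and hospitalisations for elective treatment of a pre-existing condition do not need reporting as SAEs". It is worded as an exemption from reporting, so some sites may still record the event. If not, the patient is simply a death in Table 9, with no clot or bleed shown.

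**4. Another clot or bleed, non-serious.** There is no SAE route. The general duty, "in addition to any clinically significant untoward medical occurrence", applies only if the site judges the event significant, and the steer is that "other known symptoms of COVID-19 would not normally be considered clinically significant". Because 5.1 ties the AE definition to 5.2, an event filtered out there is not an AE at all. D-dimer, platelets, aPTT, INR, fibrinogen and troponin are endpoints and are not recorded separately as AEs, so they trigger nothing. Bleeding has one objective trigger: haemoglobin below 80 g/L (Table 2, grade 3).

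**5. SAP output.** Tables 3 and 6 have no row for any type of event. Tables 4, 7 and 8 name recorded events by arm, so a count could be made by hand. Table 5 is cited in SAP 3.4, but its shell is not in the text available to me, and I conclude nothing from it.

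**Scale, on assumed rates (none is in the documents).** Expected events per arm = 30 × rate:

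| Assumed rate | Expected events in 30 |
|---|---|
| 5% | 1.5 |
| 10% | 3.0 |
| 15% | 4.5 |

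At 10%, one unrecorded event is a third of the arm's expected count. Zero events in 30 still allows a true rate up to 1 − 0.05^(1/30) = 9.5% (one-sided 95% bound).

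Power to detect 10% against 20% (two-sided 0.05, normal approximation) is Φ[(0.10 − 1.96 × √(2 × 0.15 × 0.85/30)) / √((0.10 × 0.90 + 0.20 × 0.80)/30)] = Φ[(0.10 − 0.181)/0.0913] = Φ(−0.88), or about 19%. A comparison by arm can only be descriptive.

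**The case against.** A reader might infer that pulmonary embolism, stroke and bleeding are recorded only if the investigator does not call them COVID-19. The documents do not support that:

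- Section 5.3 covers serious events whether or not they were expected, and its exemption is narrow.
- The steer in 5.2 begins with non-serious events and speaks of symptoms. Neither document calls a lung clot or a stroke a symptom.
- Section 5.2 also carries a positive duty to record anything clinically significant.
- A bleed that takes haemoglobin below 80 g/L is recorded whatever its cause.

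All of this stands, and it confines the problem to the three gaps.

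It can also be said that the missing SAP row is a matter of presentation, since 60 patients can be counted from listings. That is right for events that were recorded. It does not help with an event that was never entered, and it leaves the grouping of terms to be decided after the data are seen.

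Finally, few events mean little inference. That argues against a test, not against complete recording.

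**Conclusion.** The point holds in a limited form. Two clotting events are recorded by name. The others should mostly be caught when serious, but can be lost in three ways: as a non-serious event taken for COVID-19, as a fatal event attributed to COVID-19, or through the contradiction over expectedness between 5.1 and 5.3. The SAP has no by-arm count for any clot or bleed, so even the specific recording that 5.2 promises has no matching summary.

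The size of the loss cannot be estimated. It depends on event rates and on site habits that the documents do not give. The rates used above are assumptions and show only that counts will be small enough for one or two events to matter. The primary D-dimer analysis is not affected. This is an inexpensive improvement to safety capture and to the interpretation of the primary result.

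**What to change.** 1. **Protocol 5.2.** Extend the named list to all confirmed venous and arterial thromboembolism, including pulmonary embolism and stroke, and to clinically relevant bleeding. Record each with its onset date, whether or not it is attributed to COVID-19, and include fatal events. No extra imaging is needed.
2. **Protocol 5.1 and 5.3.** Reconcile the two sections on whether an event must be unexpected to count as an SAE.
3. **SAP 3.4.** Add one table by arm of the number and percentage of patients with any thrombosis and with any bleeding, without a formal test. Base it on all treated patients. The Full Analysis Set in SAP 2.2 requires the full course, so someone who stopped early because of a clot would drop out of it.
4. **Early clots.** At most, list patients whose clot began before the Day 3 sample, with their D-dimer values. Do not repeat the primary comparison without them. That would select on an event after randomisation that the drug may itself affect, and could remove part of the effect under study.

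The cost is a short checklist on the eCRF, a few more events to enter and one extra table.

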3.7 Additional data

Vital signs and cardiovascular monitoring will be documented at days 1, 3 and 5. (Table 12).

Table 1. Baseline characteristics

	FAS		IAS	
	Control	TRV027	Control	TRV027
	Median (range) or N (%)			
Age (yr)				
Age group				
<60				
60-69				
>69				
Gender				
Male				
Female				
BMI (kg/m²)				
Ethnicity				
White				
Mixed				
Asian				
Black				
Other				
Disease severity?				
Ie FDA grade 1-5?				

Table 2 Drug Compliance

	Control N (%)	TRV027 N (%)
Total Missed doses		
Total % Compliance		
Median missed doses per patient (range)		
Patients with missed dose due to hospital discharge		
Patients with missed dose due to death		

Table 3 Safety data – Pooled Adverse events

	Control		TRV-027	
	No. of Events	No. of Subjects*	No. of Events	No. of Subjects*
Number of Adverse events				
Severity				
Grade 1				
Grade 2				
Grade 3				
Grade 4				
Grade 5				
Missing				
AE classification				
Not serious				
Serious				
AE expectedness				
Expected				
Unexpected				
Not Applicable				
Missing				
Relation to study				
Definitely				
Probably				
Possibly				
Unlikely				
Not related				
Not assessable				
Missing				

* A patient may have several AEs

Table 4 – TRV027 Safety data –Adverse events details by patient

Control				TRV-027			
Pt ID	AE category	AE name	Grade	Pt ID	AE category	AE name	Grade

Table 6 Safety data – Serious Adverse Events

	Control		TRV027	
	No. of Events	No. of Subjects	No. of Events	No. of Subjects
Number of Serious Adverse Events				
Reasons for SAE				
Resulted in death				
Life threatening				
Congenital anomaly/birth defect				
Persistent or significant				
Disability/incapacity				
Inpatient hospitalisation/prolongation of existing				
Other				
Severity				
Mild				
Moderate				
Severe				
Life threatening				
Death				
Causal relationship to study drug				
Definitely				
Probably				
Possibly				
Unlikely				
Not related				
Not assessable				

Table 7 Safety data – Serious Adverse events details (Controls)

SAE description	SAE Term	Outcome

Table 8 Safety data – Serious Adverse events details (TRV027)

SAE description	SAE Term	Outcome

Table 9 Day 30 Survival

	Control	TRV027
Alive		
Dead		
Lost to follow-up		

Table 10 FAS Efficacy and exploratory parameters

	Control			TRV027		
	Day 1 [N=] Median (range)	Day 3 [N=] Median (range)	Difference D3 – D1	Day 1 [N=] Median (range)	Day 3 [N=] Median (range)	Difference D3 – D1
D-dimer						
Platelets						
aPTT						
INR						
Fibrinogen						

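### Endpoint laboratory tests are exempt from adverse event recording, but the SAP gives no count by arm of patients who reach a severe value on them

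*Protocol*

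**What the plan says.** Protocol 5.2 sets two rules for laboratory results.

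- Counted as adverse events: "We will record any new grade 3 or 4 laboratory abnormalities (CTCAE) in Haemoglobin, Neutrophil count, Alanine aminotransferase (ALT), Potassium, Sodium".
- Exempt because they are endpoints: "Routine observations, D-dimer, Platelets, aPTT, Fibrinogen, INR, Plasma Renin Mass, Bilirubin, LDH, Haptoglobin", continuing with "Creatinine, BNP, Ferritin, Troponin, Pro-calcitonin and Glucose will all be recorded as study endpoints and therefore not recorded separately as adverse events".

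The same section leaves a clinical route open. Anything untoward that is judged clinically significant is recorded, "Medical judgement will be used to determine clinical significance and the need to record other events as AEs", and two diagnoses are named: "We will also specifically record any incidence of deep vein thrombosis or myocardial infarction".

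In the SAP, adverse events and SAEs are tabulated by arm (Tables 3 to 8). Creatinine, bilirubin, platelets, aPTT, INR, fibrinogen and glucose appear only in the shell headed "Table 10 FAS Efficacy and exploratory parameters", which shows Day 1, Day 3 and their difference. SAP 3.3 adds, for each arm, a mean difference with a 95% CI and a between-arm test. SAP 2.2 defines the FAS as patients who received the full course.

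**The concern.** The protocol's reason for the exemption is that these results are captured as endpoints. That reason is sound only if the endpoint analysis shows what an adverse event table would have shown: how many patients in each arm developed a severe abnormality. Endpoint summaries describe the distribution of an arm, whereas severe laboratory toxicity usually affects a few patients.

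The trial tests a vasoactive drug that acts on the renin angiotensin system, in patients of whom many are expected to progress to organ failure (Protocol 4.4). Kidney injury, thrombocytopenia, rising bilirubin and deranged clotting are natural things to compare between arms. If the only tally depends on whether a clinician chose to report a clinical event, an imbalance could be missed or distorted by uneven reporting, even though the laboratory values are in the database.

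**Working it through.** The plan states no figure on this point, so there is none to reproduce. The check has two parts.

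**1. Exempt tests against the SAP table shells**

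| Question | What the SAP provides |
|---|---|
| Number per arm reaching a severe value? | None. Table 11 counts only inotrope requirement and D-dimer response. |
| Grade or shift table? | None. |
| Days 5 and 8? | SAP 3.3 says the tests are measured then and cites Tables 9 and 11. Table 9 is Day 30 survival; Table 11 has two categorical outcomes at Days 1 and 3. Table 10 stops at Day 3. |
| Patients who stopped early? | Not in Table 10, which is FAS only. The incomplete set is promised descriptive statistics, but its only shell is Table 1 (baseline). |
| SOFA, which uses creatinine, bilirubin and platelets (Protocol 3.1)? | No SAP table. |

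The remaining route is clinical reporting, and its boundaries are unclear. Protocol 5.1 defines an SAE as an unexpected event. Protocol 4.4 describes end organ failure as likely. Protocol 5.3 says of SAEs "All such events, whether expected or not, should be recorded". Sites could read these differently for the same case of kidney injury. The three passages must be reconciled.

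**2. What the planned summaries can and cannot show**

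*Median and range.* Assumed inputs: 30 patients (the planned arm size), creatinine evenly spaced from 60 to 110 µmol/L, and the k highest values replaced by 400.

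| k severe of 30 | Median | Range |
|---|---|---|
| 0 | 85 | 60–110 |
| 1 | 85 | 60–400 |
| 5 | 85 | 60–400 |
| 10 | 85 | 60–400 |
| 14 | 85 | 60–400 |
| 15 | 242 | 60–400 |

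The range shows that an extreme value occurred. From 1 to 14 affected patients the display does not change.

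*Mean.* The mean does move. With k = 1 it is (30 × 85 − 110 + 400)/30 = 94.7. It still does not give a number of patients: a mean rise of 21 µmol/L over 30 patients is a total of 630, which could be 3 patients rising by 210 or all 30 rising by 21.

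*Simulation.* Assumed inputs: median creatinine 80 µmol/L, log-SD 0.30 between patients and 0.15 per measurement, 3- to 4-fold rises in affected TRV027 patients, no affected controls, 30 per arm, 4,000 trials. Results are approximate.

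| | 3/30 v 0/30 | 6/30 v 0/30 |
|---|---|---|
| Difference in median change (µmol/L) | 2.4 | 5.1 |
| Rank test rejects | 9% | 22% |
| Difference in mean change (µmol/L) | 21 | 42 |
| Welch t-test rejects | 14% | 90% |
| Typical Day 3 maximum, TRV027 v control (µmol/L) | 369 v 157 | 425 v 156 |

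Medians and a rank test would largely miss such a pattern. The mean and the range would react to it. SAP 3.3 leaves the choice of test open.

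*Counts.* Fisher exact, two-sided: 6/30 v 0/30, p = 0.024; 3/30 v 0/30, p = 0.24; 6/30 v 2/30, p = 0.25.

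**The case against.** The plan is not blind to these patients. Ranges, differences and mean changes with 95% CIs are all planned and, as shown, would move with extreme values. Grade 3 or 4 ALT is a recorded adverse event, so hepatocellular injury is counted, and myocardial infarction is recorded by name. Any event judged clinically significant, and any SAE, reaches Tables 3 to 8 by arm. The DSMC reviews endpoints as well as safety data after every 12 patients (Protocol 5.4). SAP 2.5 also says that withdrawn patients stay in the final analysis.

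Most of this stands, and it rules out stronger readings that a reader might infer:

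- *These tests are shown only as medians, so Table 10 would look clean.* The documents do not support this, given the planned ranges and mean differences.
- *Severe kidney, liver or platelet injury is never counted.* Clinical reporting can capture it, and the liver gap is limited to bilirubin and INR.
- *A count would show harm with statistical significance.* That depends on the assumed rates. Two affected controls are enough to take 6/30 from p = 0.024 to about 0.25, and Protocol 4.4 makes zero affected controls doubtful.

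The objection does not supply the count. Ranges and means do not give numbers of patients, the clinical route is discretionary, and no count by arm is specified for the DSMC. The general statement in SAP 2.5 does not change the FAS heading of Table 10.

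**Conclusion.** The concern holds in a limited form. If the plan is followed exactly, no table gives the number of patients per arm with a severe value of creatinine, bilirubin, platelets, aPTT, INR, fibrinogen or glucose. No shell covers these tests after Day 3, and patients who stopped early are left out of the only table that does. Severe abnormalities are counted only through separate clinical reporting, under SAE passages that do not agree.

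This conclusion rests on the text of the two documents and needs no assumed rates. The creatinine figures are assumptions that show only how the summaries behave. The loss is descriptive: in an arm of 30, the median and range could be the same with 1 affected patient as with 14. It should be corrected, but it does not affect the primary analysis.

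**What to change.** The exemption from adverse event recording can stay. Add one SAP safety table by arm, as follows.

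- **Population:** all patients who received any study infusion, not only the FAS, with the number who have at least one post-baseline value.
- **Tests:** creatinine, bilirubin, platelets, aPTT, INR, fibrinogen and glucose. Troponin can be left out, since myocardial infarction is recorded by name.
- **Content:** shift from Day 1 CTCAE grade to worst grade on Days 3, 5 and 8, and the number (%) reaching a new grade 3 or 4. Use the CTCAE version already named in SAP 3.4.
- **Use:** descriptive, without a significance claim, and supplied to the DSMC at its planned reviews.

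Also correct the table references in SAP 3.3, and reconcile Protocol 4.4, 5.1 and 5.3 on whether expected organ failure is an SAE.

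The cost is one extra table and short text edits. All seven tests are already scheduled at Days 1, 3, 5 and 8 in Protocol Table 1, so the new table needs no extra sampling and adds no adverse event reporting.
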